This search will use ICD-10 codes as defined by the UK biobank Outcome Adjudication Group (Definitions of Stroke for UK Biobank Phase 1 Outcomes Adjudication Date: August 2017 Version: 1.1 https://biobank.ndph.ox.ac.uk/showcase/showcase/docs/alg_outcome_stroke.pdf). This will identify the following events:

- 1. Admission to hospital with aneurysmal subarachnoid haemorrhage (I60.0-I60.7)
- 2. Occlusive treatment of aneurysm.
- 3. Death diagnosed as subarachnoid haemorrhage in parts 1a-c of the death certificate.

All patients identified from the HES search with any of the above events will then have their medical notes re-evaluated by the local neurosurgery unit to confirm the HES report has accurately identified the event as aneurysm rupture or treatment.

A similar search will be repeated in Wales using NWIS/PEDW where NHS numbers are also used. Scotland does not use NHS numbers making searches more complex. However, a further search of equivalent database (SMR01) will be performed in Scotland using name and date of birth for identification.

Data collection - quality assurance - central HES ONS data

Additionally, all patients will be checked for possible SAH events that could have been miscoded.

Therefore, any patients with the codes:

- 1. Subarachnoid haemorrhage (other and unspecified) (I60.8-60.9)
- 2. Intracerebral haemorrhage (including intraventricular haemorrhage (I61.0-61.9)
- 3. Non-traumatic subdural haemorrhage (I62.00-I62.02)
- 4. Traumatic subarachnoid haemorrhage (S06.6X0, S06.6X9A, S06.6X9, S06.6X8A)

will have their casenotes reviewed for evidence the haemorrhage was aneurysmal.

Any patients with the following codes:

- 5. I46.1 sudden cardiac death
- 6. R96 other sudden death cause unknown
- 7. R98 unattended death

will have their casenotes reviewed to assess if their death was likely due rupture of their aneurysm.

Additionally, in at least one pilot site, all patients with the code

8. Cerebral infarction (63.0-63.9 & I64.X)

will have their casenotes reviewed to estimate rates of missed diagnosis for the whole cohort.

Where verification cannot be established from medical notes, any patients with codes in the specified possible miscoded SAH events will be assumed to be non-aneurysmal unless they have a procedure code indicating occlusive treatment of aneurysm within 30 days after the event, or they were coded as

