subarachnoid haemorrhage other or unspecified and they subsequently died within 30 days (based on the very low rate of mortality from non-aneurysmal SAH) and did not have any additional codes for trauma indicating a non-aneurysmal event.

Data collection - other considerations - central HES ONS data

Last follow-up for each patient will be set as the time at which the HES search was performed, or the patient was unregistered with a GP in the UK or date of death, or the aneurysm was treated, whichever is earliest.

Additionally, we will record

- 1. race
- 2. I10 essential (primary) hypertension
- 3. Z72.0 tobacco use
- 4. F17.2 tobacco dependence

And use these to complete any missing baseline data. Where baseline data and HES conflict, the baseline data will be used. Where neither is available, after assessment for any bias (missing completely at random MCAR, missing at random MAR, missing not at random MNAR) multiple imputation will be used.

Statistical analysis - Aim 1 - PHASES validation

The PHASES study provides the coefficients from their Cox regression model and baseline survival at 5 years that allows the absolute 5-year risk of rupture, to be calculated for all patients who are not censored before 5 years, using age, whether the patients has hypertension, history of SAH, size of aneurysm (3 categories) and location of aneurysm. The time to censoring will be calculated (death or date of HES search or date unregistered from GP practice whichever is first) to ensure 5 years of follow up if rupture has not occurred. Discrimination will be assessed using Harrell's C-index of concordance and Royston and Sauerbrei's D statistic. Calibration will be assessed at the 5 year time point using the method in Royston (2014). These will be used to calculate the number of SAH events per 5 years for each PHASES score (0 to 12+) and expressed as a percentage with 95% confidence interval to compare to the PHASES estimates.

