7.2 Sampling

7.2.1 Size of sample

Sample Size

There are no accepted methods for power calculation for validation studies of prognostic models. Therefore, usually the rule of thumb to have ten events for every covariate tested is applied.

For Aim 1, 6 covariates will be tested suggesting at least 60 SAHs will need to be captured. ISUIA recorded 51 ruptures in 1692 patients over 4.1 years. Sixty events may therefore be expected in 1,990 patients with 8,161 years of follow up.

For Aim 2, 120 events will need to be observed to account for the 6 additional commonly occurring covariates which would be expected in 3,981 patients with 16,332 years of follow up.

For autosomal dominant polycystic kidney disease (ADPKD) which has a low incidence, larger numbers of patients will be needed. Ten events in ADPKD are expected in 1360 patient years of follow up assuming the risk of SAH is not elevated and similar to the general population. However, 16,332 years follow up would only yield 195 years in patients with ADPKD (based on a population study which found 53/4436 IAs had ADPKD (Nurmonen 2017) and consistent with pilot data where 11/1025 cases examined to date had ADPKD). Therefore 113,905 years of follow up would be required to capture 10 ruptures amongst 1,340 years follow up in ADPKD patients. This would equate to 22,781 patients with 5 years of follow up (or applying the slightly looser rule of 5 events per prognostic factor this would require 56,952 years of follow up with 11,391 patients).

In a local pilot 1,415 cases were identified over 14 years in a population of 3 million with an anticipated 6,000 years of follow up. Extrapolating to England, Wales and Scotland 31,130 patients with 132,200 years follow up are available - well in excess of the target of 8,161 to validate PHASES in the general population, as well as the 16,332 to test the additional variables, but only just sufficient to answer the role of rarer predictors such as ADPKD. For reference PHASES was based on 29,166 years of patient follow up. Therefore, all cases that can be identified in England and Wales will be sought up to a maximum of 22,781.

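### Follow-up closes at the HES search date, not at the date to which each linked source is complete, so any reporting lag is counted as event-free time

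*Protocol*

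**What the plan says.** Section 5 of the protocol, under other considerations for the central HES and ONS data, gives the closing rule: "Last follow-up for each patient will be set as the time at which the HES search was performed". The rule allows earlier closure for three reasons only: GP deregistration, death and aneurysm treatment. The paragraph on the Aim 1 analysis gives a similar list, "death or date of HES search or date unregistered from GP practice whichever is first", and uses it to establish who has 5 years of follow-up.

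The sources are not one database. Deaths come from ONS. For the other nations, "A similar search will be repeated in Wales using NWIS/PEDW where NHS numbers are also used", and "a further search of equivalent database (SMR01) will be performed in Scotland using name and date of birth for identification". The closing rule names only the HES search. The protocol states no date to which HES, ONS, PEDW or SMR01 records are complete.

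The Aim 1 text accepts that rupture risk may be underestimated and lists corrections: unrecorded emigration, miscoding, failed verification of codes, and a comparison of HES with local notes. A gap between the end of the data and the search is not on the list. Aim 3 adds that HES searches will be repeated periodically.

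**The concern.** A linked event can be found only if it falls on or before the last date to which the source is complete. If that date precedes the search, the days between are time at risk in which a rupture would not be seen. Under the stated rule, a patient still open at the search contributes that time to the denominator and nothing to the numerator. A patient who dies or is treated within the gap may also be carried on as open. The error has one direction: rates and absolute risks come out too low.

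The effect is not even over follow-up. Late follow-up is contributed only by early entrants, and a growing share of it lies close to the search. A constant hazard would therefore appear to fall with time since diagnosis, and Aim 3 uses a cumulative hazard plot to judge exactly that. In Aim 1, a patient truly observed for slightly less than 5 years would be counted as having the full 5. The same error would return at each repeat search.

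**Working it through.** **Inputs from the protocol (section 7.2.1).** The planning rate comes from "ISUIA recorded 51 ruptures in 1692 patients over 4.1 years": 51/(1,692 × 4.1) = 0.735% per patient-year. Then 60/0.00735 gives about 8,161 patient-years, which reproduces the Aim 1 target. The sample size is not in question here. Mean follow-up is 6,000/1,415 = 4.24 years in the pilot and 132,200/31,130 = 4.25 years when extrapolated.

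**Assumptions.** The lag L is not in the documents, so 3, 6 and 12 months are tried. Steps 1 to 3 take uniform entry over 15 years with the search at the end, except where stated.

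1. *Crude rate.* Let p be the share of patients still open at the search and m the mean follow-up.
   - The empty share of person-time is pL/m if m already includes the gap, and pL/(m + pL) if it does not.
   - With a constant exit rate c, p = (1 − e^(−15c))/(15c) and m = (1 − p)/c. Setting m = 4.24 gives c ≈ 0.1345 and p ≈ 0.43. Check: (1 − 0.43)/0.1345 = 4.24.
   - With the gap included in m: 0.43 × 0.25/4.24 = 2.5%, 0.43 × 0.5/4.24 = 5.1% and 0.43 × 1/4.24 = 10.1%.
   - With the gap excluded: 2.5%, 4.8% and 9.2%.
   - Entry over the pilot's 14 years gives p ≈ 0.47, hence 2.8% at 3 months and 11.1% at 12 months.
   - The upper limit is every patient open (p = 1, m = 4.25, gap excluded): 5.6%, 10.5% and 19.1%.

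2. *Hazard by time since entry, and 5-year risk.* Patients at risk at time t entered over a span of 15 − t years, and a span of L years of them is inside the gap.
   - The hazard at t is diluted by L/(15 − t). Exits unrelated to entry date cancel out.
   - For a 6-month lag: 0.5/10 = 5% at year 5 and 0.5/5 = 10% at year 10.
   - Averaged over years 0 to 5, the dilution is (L/5) × ln(15/10) = 0.081L, that is 2.0%, 4.1% and 8.1% for 3, 6 and 12 months.
   - A simulation with constant hazard 0.735% per year, no other exits and the search half a year after entry closes agrees. The 5-year risk of about 3.6% becomes 3.55%, 3.48% and 3.33%. The 10-year risk of about 7.1% becomes 6.93%, 6.76% and 6.40%.
   - With other exits at 15% per year (assumed), the falls are similar.

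3. *Aim 1 limited to patients with 5 years of potential follow-up.* Entry then spans 10 years, giving 10 × 5 = 50 units of person-time.
   - Only those entering within L of the 5-year boundary are affected, each by L/2 on average, so the empty time is L²/2.
   - This gives 0.03125/50 = 0.06% at 3 months and 0.5/50 = 1% at 12 months.

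4. *Do the planned corrections reach the gap?* The emigration and miscoding adjustments concern other mechanisms. The comparison with local notes uses follow-up recorded at baseline data collection, and the HES search is run only after all baseline data are in. Those notes therefore stop before the search and are not a systematic check on the period just before it.

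**The case against.** The strongest objection is that the premise is not in the protocol. Nothing there says that any source is incomplete at the search date, and the search date may be shorthand for the data cut, with the exact date fixed in a later specification. The first half stands: the bias is conditional, and with zero lag there is none. The second half weakens the point but does not remove it, because the protocol does name a closing date, names it twice, and names only the HES search although Wales and Scotland are searched separately.

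A reader might infer that every surviving patient gains empty time. The general rule does not support that. Survivors with a recorded treatment or GP deregistration close earlier, and patients with a recorded rupture are not extended. Nor is it right that no event at all could be seen, since local notes also record haemorrhage, death and treatment, though for quality control and before the search.

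A reader might also infer larger losses by supposing that 70% of patients are still open: 0.7 × 1/4.24 = 16.5% at 12 months. The documents give no such share, and it does not fit uniform entry and a constant exit rate with a 4.24-year mean, which imply about 43%. A larger share is possible if entry rises over time.

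Finally, a reader might conclude that PHASES will be made to look over-predicting. That is not shown. The Aim 1 text confines the 5-year calculation to patients not censored before 5 years. If this means 5 years of potential follow-up, the effect there is at most about 1% for the lags tried. Other readings of that sentence are possible.

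**Conclusion.** The point holds in conditional form. The closing rule is stated and is wrong in principle, because it ties the end of follow-up to the day of the query and not to the end of the observable period, and it applies one source's date to patients followed in several. If any source ends before the search, rates are biased downward and the late hazard appears to decline. None of the listed corrections addresses this.

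The size rests on an assumed lag. At 3 to 12 months it is roughly 2.5% to 10% of the crude rate with about 43% of patients open, and more if more are open. It is about 2% to 8% of a Kaplan-Meier 5-year risk, which matters mainly for Aims 2 and 3, and possibly only 0.06% to 1% in Aim 1. The shape of the hazard in Aim 3 is the most exposed result: about 5% dilution at year 5 and 10% at year 10 for a 6-month lag. All percentages are relative, and all depend on the entry and exit patterns assumed above.

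**What to change.** Replace the search date in the closing rule by a completeness date. For each patient, set administrative censoring at the documented date to which the extracts for that patient's nation are complete, taking the earlier of the admissions and death-registration dates. Keep the existing earlier closing events. Disregard any event after that date, so that numerator and denominator cover the same period. Use the same date in the Aim 1 censoring definition, including the test for 5 years of follow-up, and reset it at each repeat search. Report the dates by source.

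This takes one sentence in the protocol and no extra data. The cost is a few months of nominal follow-up and any events recorded after the completeness date. If the extracts turn out to be complete to the day of the search, the change has no effect.

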4 RESEARCH QUESTION/AIM(S)

Primary Aims:

Aim 1 - To validate the PHASES score in a UK population.

- Aim 2 To develop a new prediction model including all described predictors of risk.
- Aim 3 To report long-term risk of aneurysm rupture.

Secondary Aims:

Aim 4 – To develop risk models of aneurysm growth.

Aim 5 – To evaluate the efficacy of aneurysm screening regimens.

Aim 6 – To develop and evaluate new radiological predictors of aneurysm growth and rupture.

5 STUDY DESIGN and METHODS of DATA COLLECTION AND DATA ANALYIS

Data Collection – Baseline data – local neurosciences units Patients will be identified by members of the clinical care team and record:

- NHS number
- Name
- Date of birth
- Post code

These patients will be allocated a study number for pseudonymisation. This data will not be otherwise kept or used for other research purposes.

Further data will be collected from patient's case notes (either electronic or paper based as appropriate). A separate data definitions manual will be produced. All data collectors will be provided with a mandatory education module and correctly collect data from test cases before data collection.

The core covariates for each patient at time of diagnosis will be:

- Date of first diagnosis of aneurysm (date of first CTA/MRA/DSA or where not available date of first MDT or clinic appointment whichever is earlier)
- Date of inclusion in the study (date of first CTA/MRA/DSA or where not available date of first MDT or clinic appointment that lies within the unit's search period)
- Hypertension: a co-morbidity of hypertension or regular use of anti-hypertensive medication at time of diagnosis.
- Age: in years at time of diagnosis of aneurysm on angiographic imaging
- Gender:
- Site: anterior cerebral artery (including anterior communicating and pericallosal arteries), internal carotid (including bifurcation, ophthalmic, superior hypophyseal), MCA (including M1 segment and bifurcation), posterior communicating and posterior circulation (including vertebral, basilar, cerebellar and posterior cerebral arteries).
- Aneurysm size: the longest aneurysm dimension recorded to the nearest millimetre as described by the MDT discussion or where not available from the reporting radiologist at time of diagnosis or where not available from the clinic letter.
- Previous aneurysmal subarachnoid haemorrhage: confirmed diagnosis of aneurysmal SAH in the patient's medical history.

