- Population: European/North American, Finnish, Japanese (where race cannot be confirmed it will be assumed to be non-Finnish and non-Japanese on the basis that there is a low incidence of these populations in the UK and their presence would usually be considered noteworthy in a clinical note.

The additional desirable covariates at time of diagnosis will include:

- aspirin use any dose used >3* per week
- statin use any statin use >3* per week
- smoking history non-smoker, ex-smoker, current smoker
- Aneurysm multiplicity record number of intra-dural aneurysms the patient has (treated or untreated)
- Family history number of 1 first degree and second degree relatives with UIA/SAH
- History of Autosomal Dominant Polycystic Kidney Disease yes, no
- Aneurysm location subclassification ICA paraclinoid (ophthalmic and superior hypophyseal) ICA (PCom), ICA other (anterior choroidal and bifurcation), ACA ACOM, ACA pericallosal, MCA, Posterior (basilar termination), Posterior (SCA), Posterior (AICA) Posterior (PICA)
- Bleb or irregularity of aneurysm recorded as present or absent from radiology report only. If not mentioned in report assumed to be absent. If no radiology report available, then recorded as NA.
- New/known diagnosis: patients in whom the aneurysm was known prior to the search period will be recorded as known diagnosis and otherwise as new diagnosis.

Data collection – aneurysm rupture/censoring events – local neurosciences units

At the time of baseline data collection locally available follow up will be recorded which will include:

• Date of last follow-up

- Date of death (if applicable)
- Cause of death (if applicable)
- Date of SAH (if applicable)
- Location of aneurysm causing SAH (if applicable)
- Date of aneurysm treatment (if applicable)
- Reason for aneurysm treatment (if applicable)

This data will be used for quality control of subsequent HES searches.

Data collection - aneurysm rupture/censoring events - central HES ONS data

Upon collection of all baseline data, a search of the Hospital Episode Statistics (HES) and Office for National Statistics (ONS) databases using the patient's NHS numbers be conducted. The use of a HES and ONS search is designed to maximise the identification of rupture events which are not treated in neurosurgical unit as subarachnoid haemorrhage. It will thus identify events managed in a district general hospital or those who die pre-hospital.

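### Presence-only HES codes fill missing hypertension and smoking before imputation, with no rule for a missing code, so completed prevalence is biased low or high depending on how the rule is read

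*Protocol*

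**What the plan says.** Protocol section 5, *Data collection - other considerations - central HES ONS data*, lists race and three diagnosis codes to be taken from HES: "I10 essential (primary) hypertension", "Z72.0 tobacco use" and "F17.2 tobacco dependence". It then fixes an order of steps:

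- The HES items come first: "And use these to complete any missing baseline data".
- The notes win any disagreement: "Where baseline data and HES conflict, the baseline data will be used".
- Multiple imputation comes last, for what remains: "Where neither is available, after assessment for any bias", with an assessment of the missing-data mechanism beforehand.

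The variables to be filled are defined earlier in section 5. Hypertension is "Hypertension: a co-morbidity of hypertension or regular use of anti-hypertensive medication at time of diagnosis". Smoking has three levels: "smoking history non-smoker, ex-smoker, current smoker".

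Section 3 explains that the national databases hold diagnoses coded at hospital admissions, and that most patients with an unruptured aneurysm are managed as outpatients. The Aim 2 analysis text repeats that multiple imputation will be used but does not name the predictors in the imputation model.

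**The concern.** Each of the three codes can say only 'yes'. None of them marks a patient as free of hypertension, a never-smoker or an ex-smoker. A patient who was never admitted cannot carry a code at all, so missed codes are built into the source. The plan does not say whether a linked patient with no code counts as having HES data (and is therefore a 'no') or as having none (and therefore goes to imputation).

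Hypertension enters the PHASES risk in Aim 1, and smoking is one of the additional predictors named for Aim 2. If the completion step shifts either distribution systematically, predicted risks and smoking categories shift with it. The shift would come from a step written into the protocol, so an analysis plan that follows the protocol would inherit it.

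**Working it through.** The protocol states no prevalence, missing share or code sensitivity, so there is no figure of its own to reproduce. All inputs below are assumptions: true prevalence p = 0.40, code sensitivity s, no false-positive codes, and share missing from the notes m, missing at random.

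**Patients missing from the notes.** The fill captures ps of them as 'yes'. True prevalence in the uncoded remainder is p(1 - s)/(1 - ps).

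- Reading A (no code = 'no'): completed prevalence = ps.
- Reading B (no code = still missing, imputed at the prevalence in the notes, code not used): ps + (1 - ps)p.

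| s | True prevalence in uncoded remainder | A | B | Truth |
|---|---|---|---|---|
| 0.4 | 0.24/0.84 = 29% | 16% | 0.16 + 0.84 × 0.4 = 50% | 40% |
| 0.6 | 0.16/0.76 = 21% | 24% | 0.24 + 0.76 × 0.4 = 54% | 40% |
| 0.8 | 0.08/0.68 = 12% | 32% | 0.32 + 0.68 × 0.4 = 59% | 40% |

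**Whole cohort, m = 0.30, s = 0.6.**

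- A: 0.7 × 0.40 + 0.3 × 0.24 = 0.352, about 35%.
- B, imputing at 40%: 0.28 + 0.3 × 0.544 = 0.443, about 44%.
- B, imputation fitted to the already filled data: (0.28 + 0.072)/(0.70 + 0.072) = 0.352/0.772, about 46%.

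**Range.** Over p = 0.2 to 0.5, m = 0.1 to 0.4 and s = 0.3 to 0.9, A is low by p·m·(1 - s), that is by 0.2 to 14 points. B, fitted to the filled data, is high by 0.5 to 11.5 points. Better coding does not cure B: at s = 1, p = 0.40 and m = 0.20 it gives 0.40/0.88 = 45.5%.

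**Smoking.** Assume never/ex/current 40/30/30, m = 0.20, 60% of current smokers coded and ex-smokers never coded. The fill captures 0.3 × 0.6 = 0.18 of the missing group.

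- A: 0.32 + 0.2 × 0.82 = 48.4% never, 24.0% ex, 0.24 + 0.2 × 0.18 = 27.6% current.
- B: the known values 0.32, 0.24 and 0.276, divided by their sum 0.836, give 38.3%, 28.7% and 33.0%.

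The codes recover no ex-smoker under either reading. Under B, imputation still assigns that level.

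**Effect on hazard ratio and predicted risk.** Assume a hazard ratio of 1.40, m = 0.30, s = 0.6, and sensitivity unrelated to outcome. Under A, the patients classed 'no' include 0.4 × 0.3 × 0.4 = 0.048 true hypertensives out of 0.648, or 7.4%. The ratio becomes 1.40/(1 + 0.40 × 0.074) = 1.36. Simulation gives 1.36 for A and 1.41 for B. Mean relative hazard is 1 + 0.4 × prevalence: 1.160 at truth, 1.141 under A (-1.7%), and 1.177 to 1.182 under B (+1.5% to +1.9%).

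**With the code as a predictor in the imputation model.** Uncoded patients are drawn at p(1 - s)/(1 - ps) = 0.2105, learned from patients who have notes. The missing group becomes 0.24 + 0.76 × 0.2105 = 40%. In simulation with event status in the imputation model, the hazard ratio also returned to its true value.

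**The case against.** The strongest reply is that the protocol does not specify the imputation model, and its predictors are usually left to the analysis plan, which is not shown. The imputation clause also fits 'still missing' better than 'no', because under 'no' every linked patient would have a value and imputation would hardly be used for these variables. If the code is a predictor in that model, the bias under this reading disappears. This stands. The high prevalence is conditional on the code being left out, and a reader who infers that the result must be wrong under either reading goes further than the text allows.

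Three other stronger readings also fail.

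- A reader might infer that the fill makes the remaining data missing not at random. On the assumptions used here, whether a value is still missing after the fill depends on the code, which the study records. The remainder is therefore missing at random given the code.
- A reader might infer that ex-smokers cannot be identified. The notes supply all three levels and override HES. Only patients without smoking status in the notes are affected, and uncoded ex-smokers are lost only if no code is read as non-smoker. An ex-smoker who carries a tobacco code would be filled as a user.
- A reader might infer serious distortion of hazard ratios or calibration. With sensitivity unrelated to outcome, the figures do not show it. Coding that depends on rupture would matter more, and the section sets no date limit on the codes, but that is a separate question of timing on which this point does not rest.

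It can also be said that the fill is harmless when codes have no false positives, and need only be supplemented by the code as a predictor. For hypertension, on that assumption, this is right. It does not cover a coded ex-smoker.

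**Conclusion.** The point holds in limited form. The protocol prescribes a presence-only fill followed by imputation of the remainder and leaves the meaning of an absent code open. Completed prevalence is too low if absence is read as 'no'. It is too high if absence is read as missing and the imputation omits the code. On the assumed 40% prevalence, 60% sensitivity and 30% missing, the cohort figure is about 35% or 44 to 46%.

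The real size depends on the share missing, which the protocol does not give; if few notes lack these items, the error is small. The consequence for hazard ratios and mean predicted risk is probably small as well, provided coding does not depend on outcome. This is a cheap improvement to a stated step and no threat to the study's main conclusions.

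**What to change.** In section 5, state that absence of an I10, Z72.0 or F17.2 code does not mean 'no'. Replace the direct fill for hypertension and smoking with this rule: an indicator for the hypertension code and one for either tobacco code enter the planned multiple-imputation model as predictors of hypertension and of three-level smoking, alongside the outcome. The weight given to a code, or to its absence, is then learned from patients who have both notes and HES, and the ex-smoker level is imputed from the observed three-level distribution. Race is not a presence-only item and is not affected.

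The cost is a change of wording and slightly wider intervals than a hard fill would give. The HES fields are already requested and imputation is already planned, so no new data are needed.

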3 THEORETICAL FRAMEWORK

The study is designed as a UK based multi-centre study which incorporates retrospective patient identification combined with outcomes recorded in a prospective database.

NHS Health Research Authority

The first stage of the study is for individual neurosurgery units to identify their patients with an unruptured aneurysm and collect baseline data about that aneurysm. Most patients with unruptured aneurysms are managed as outpatients and assessed in a neurosciences unit in the UK. This should identify a large cohort of patients and the necessary aneurysm variables to predict risk are best recorded in local medical notes.

Searches will be done retrospectively over a period of up to 2006-2020. Patients can be identified from sources such as clinic letters, MDT discussions or radiology reports. A retrospective design allows the identification of patients diagnosed up to 15 years ago and thus the length of follow-up achievable will exceed the 5 years currently used in PHASES. Given that UIA can rupture at any point in a patient's lifetime the longer the follow-up achieved will make the results more translatable to the actual patient. Trying to achieve the same length of follow-up with a prospective study would take considerably more time and financial investment.

This study is best done as a multi-centre design because of the large number of patients required. UIA rupture is uncommon (approximately 1% per year) and thus to reach the minimum number of ruptures required to test the current PHASES model a much larger overall cohort of UIA will be required. This is only realistically achievable by many neurosurgical units pooling their patient numbers.

The second stage in this study is to compile the patients into a single cohort and link them to national databases for hospital admissions (HES/PEDW/SMR) for the UK. Every hospital admission in the country is recorded on one of these databases with the corresponding codes for diagnosis during that admission. Searching the cohort against these databases will return all admissions following diagnosis of a ruptured aneurysm.

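### Missing baseline hypertension and smoking are filled from HES codes of any date, so codes recorded after inclusion, even at the rupture admission, can become baseline values

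*Protocol*

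**What the plan says.** Section 5, baseline data collection, defines hypertension as "a co-morbidity of hypertension or regular use of anti-hypertensive medication at time of diagnosis". Smoking, with three levels, is listed among the additional covariates that are also fixed at diagnosis.

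Section 5, other considerations for the central HES and ONS data, lists race, "I10 essential (primary) hypertension", "Z72.0 tobacco use" and F17.2 as items to record, and continues: "And use these to complete any missing baseline data". Two rules follow. The local record wins a disagreement: "Where baseline data and HES conflict, the baseline data will be used". Multiple imputation applies to what is left: "Where neither is available, after assessment for any bias". No date window for the codes appears there or elsewhere in the protocol. Nor does the protocol say whether the absence of a code counts as *no* or as not available.

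The HES search is run once all baseline data are in, and it is the same search that finds SAH admissions and occlusive treatments. Section 3 says that searching the cohort "will return all admissions following diagnosis of a ruptured aneurysm". That sentence is about outcomes, not covariates, but it confirms that rupture admissions are in the returned data.

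**The concern.** The covariate definitions look back from diagnosis, while the filling rule, followed as written, looks at the whole record. Hospital codes arise when patients are admitted, and a rupture that reaches hospital is itself an admission at which comorbidities are coded. For a patient whose local record is missing, the chance of becoming *hypertensive* or *smoker* at baseline then depends partly on whether the aneurysm ruptured and partly on how long the patient was followed. Conditions that began after baseline can be back-dated. A code can only show presence: Z72.0 and F17.2 cannot identify a non-smoker or separate an ex-smoker from a current one.

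Hypertension is a PHASES item, and both variables are candidates for the new Cox model. Nothing planned repairs the problem:

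- The conflict rule protects only values that were recorded locally.
- Imputation comes after filling and takes the filled values as true.
- The bootstrap resamples the same values.
- Neither Aim 2 sensitivity analysis leaves HES filling out.

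**Working it through.** **Plan figure.** The rupture rate implied by Section 7.2.1 is 51 / (1,692 × 4.1) = 0.00735 per year. Then 60 / 0.00735167 = 8,161 years, as stated. I use this rate below.

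**Inputs the documents do not give (assumed).** Prevalence p = 40%. Missing fraction m = 5%, 20% or 40%. A code before inclusion in 30% of exposed patients. Coding in follow-up at 0.02 (sparse), 0.1 (moderate) or 0.3 (frequent) per year. Coding of exposed patients at the rupture admission 80%. Death before hospital in 12% of ruptures. Time from inclusion to HES search uniform from 0.1 to 15 years.

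**Hand check of the mechanism.** Take a true ratio of 1.0 and read no code as *no*. Let s1 and s0 be the chance that an exposed patient with a missing value has a code, in ruptured and intact patients. The recorded prevalence is p[(1 − m) + m·s], with s = s1 or s0. With sparse coding and m = 40%:

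- s1 = 1 − 0.7 × (1 − 0.88 × 0.8) = 0.793, ignoring the ruptured patients' other follow-up codes
- s0 = 1 − 0.7 × exp(−0.02 × 7.55) = 0.398
- ruptured: 0.4 × (0.6 + 0.4 × 0.793) = 0.367
- intact: 0.4 × (0.6 + 0.4 × 0.398) = 0.304
- odds ratio: (0.367/0.633) / (0.304/0.696) = 1.33

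**Simulation with follow-up time.** 3,000,000 patients per scenario, exponential rupture times, and the person-time rate ratio standing in for the Cox hazard ratio. An absent code is read as *no* or imputed within strata of outcome and time. Each cell gives *no* / imputed.

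| True | Missing | Other coding | Any date | Up to inclusion |
|---|---|---|---|---|
| 1.0 | 5% | moderate | 1.02 / 1.02 | 1.01 / 1.01 |
| 1.0 | 20% | moderate | 1.07 / 1.05 | 1.01 / 1.02 |
| 1.0 | 20% | moderate, new onset 3% per year | 1.06 / 1.03 | 0.99 / 0.99 |
| 1.0 | 20% | sparse | 1.14 / 1.08 | 1.00 / 1.00 |
| 1.0 | 20% | frequent | 1.01 / 1.01 | 1.01 / 1.01 |
| 1.0 | 40% | sparse | 1.32 / 1.20 | 1.00 / 0.99 |
| 1.0 | 40% | sparse, 20% of unexposed coded at rupture | 1.56 / 1.34 | 1.00 / 1.01 |
| 1.0 | 40% | frequent, new onset 3% per year, weaker rupture coding* | 0.94 / 0.97 | 1.00 / 1.00 |
| 1.4 | 20% | moderate | 1.47 / 1.45 | 1.35 / 1.40 |
| 1.4 | 40% | sparse | 1.79 / 1.67 | 1.31 / 1.40 |
| 1.4 | 40% | frequent, new onset 3% per year, weaker rupture coding* | 1.30 / 1.35 | 1.32 / 1.40 |

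*50% coded at the rupture admission, 30% dead before hospital.

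The hand value of 1.33 agrees with the simulated 1.32. The ratio falls below the truth when patients who stay rupture-free for long have more time to collect codes, which moves event-free person-time into the exposed group.

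**Is removing the rupture admission enough?** No. With moderate coding, keeping other follow-up codes but dropping those of the rupture admission turned a true 1.0 into 0.94 / 0.96 at 20% missing and 0.89 / 0.92 at 40%. The cut has to be at inclusion.

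**The case against.** **The text does not say that rupture-admission codes are used.** This is right. The codes are to complete baseline data, the covariates are fixed at diagnosis, and a data definitions manual is promised. An analyst could infer a look-back limit from this, and a manual or SAP not seen here may set one. What remains is that the protocol states the filling rule itself, without a limit, over an extract that contains those admissions. Such codes are eligible, which is all that is claimed.

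**A reader might infer that the hazard ratios are necessarily inflated.** The documents do not support that. Not every rupture produces an admission, since Section 5 expects deaths before hospital. Intact patients are admitted too, including for aneurysm treatment. With 30% treated and 20% missing, a true 1.0 became 1.05 / 1.03. With frequent coding the bias vanishes or turns downward.

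**A reader might infer that the PHASES validation yields biased hazard ratios.** It does not. Aim 1 applies published coefficients and re-estimates none, and smoking is not a PHASES item.

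**The missing fraction may be small.** This stands as a limit on size. Hypertension is a core covariate collected by trained staff, and at 5% missing the effect is trivial.

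**An absent code most naturally means not available.** If so, the imputed figures apply and the larger ones fall away. The protocol leaves this open, and the imputed figures still move away from the truth.

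**Conclusion.** The point stands as a defect in a stated rule. As written, the rule admits codes dated after inclusion, including those of the rupture admission, as baseline values, against the protocol's own definitions. Misclassification then depends on outcome and follow-up time.

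The bias is probably upward when other admissions are few, but its direction is not fixed. For a true hazard ratio of 1.0 the estimates were about 1.02 at 5% missing. At 20% missing they were 1.03 to 1.07 with moderate other coding, about 1.01 with frequent coding and up to 1.14 with sparse coding. At 40% missing they ran from 0.94 to 1.3, and to 1.56 with false-positive coding at rupture. All of these rest on assumed prevalence, coding and missingness, none of which the documents give. Hazard ratios are affected in the fitted Aim 2 and Aim 3 models. In Aim 1 only hypertension is affected, through calibration and discrimination, and I have not put a figure on that.

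Limiting codes to inclusion returned 0.99 to 1.02 in every null scenario. With a true 1.4 it gave about 1.40 when absent codes were imputed, but 1.31 to 1.35 when they were read as *no*.

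**What to change.** Amend the filling rule in Section 5 as follows:

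- Use I10, Z72.0 and F17.2 only from episodes that start on or before the date of inclusion. Cutting on the start date keeps the admission at which the aneurysm was found; cutting on the end date would lose it.
- Never use a code from the SAH admission or any later episode.
- Treat an absent code as missing for multiple imputation, not as *no*.
- Add a sensitivity analysis without HES filling. Filling in one direction only also shifts prevalence slightly. With p = 40%, m = 20% and 30% coded beforehand, prevalence among known values is (0.32 + 0.024) / (0.80 + 0.024) = 41.7%.
- Race may be taken from any date.

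For patients whose aneurysm was already known, inclusion comes after diagnosis, so the protocol should say that the inclusion date governs. Codes between the two dates precede follow-up and do not depend on the outcome.

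The HES, PEDW and SMR requests must ask for dated episodes from before inclusion. This is a somewhat wider request, to be justified under the data-minimisation commitment, and slightly more values are left to imputation. It should be settled before linkage, because Section 8.6 puts the fee for a linkage event at £10,000.
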